### **Data Collection:**

Several types of data will be collected. The first includes demographic data on patients including age, sex, allergy history, history of EoE. Routine pathology data will be collected based on biopsy findings. Cytology specimens will be analyzed both at Mayo Clinic, Rochester and [name] lab at the University of Cambridge, looking at reproducibility.

Two center site for conduction of the Cytosponge and eosinophilic esophagitis trial, [name] at the University of North Carolina and I have agreed that we will pool our data for this study. This is thought best as we will use the same methodology and we will each collect mutually needed data to perform the study. We will not be using the exact same data collection forms, however, as both Mayo and UNC have their established data bases for eosinophilic esophagitis where there are subtle differences in some of the types of data collected. On the other hand, the data that is needed for this two center study will be collected in an identical fashion.

When the Cytosponge is taken out of the patients' mouth, washed with sterile PBS, followed by centrifugation. The supernatant will be stored at -80oC for extra-cellular RNA signature analysis with possible detection of EoE specific lumen protein products proposed. The pellet will also be subjected to total RNA extraction immediately after the supernatant aspiration. The resulting RNA will be used for microRNA array and for a qPCR based array on representative EoE mRNA signature transcripts. Both methods are mature approaches regularly performed in the [name] laboratory and have been validated with multiple cohorts, forming the foundation for diagnostic purposes.

We will extract RNA from the remaining of FFPE sponge, aiming to acquire the RNA from the residue tissue after histological examination. The RNA isolated this way will be subjected to the same experiments as the fresh wash pellet cells.

In order to validate the proposed new method, we also aim to acquire FFPE RNA from the concurrent biopsy taken by EGD if available, as biopsy tissue represents the source of the dislodged cells/tissue pieces by the cytosponge. Parallel comparison will provide key clue to validate the new diagnostic approach.

We will make parallel comparisons of EPX staining from the Cytosponge and esophageal biopsy specimens. We will also assess correlations between EPX stains and peak eosinophil counts from the corresponding H+E stain.

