### **Methods:**

- Patients with eosinophilic esophagitis and health controls, (patients without esophageal symptoms such as GERD or dysphagia), will be enrolled.
- Patients with EoE will be having a clinically indicated upper endoscopy and biopsies either for initial diagnosis or for monitoring the activity of their disease.
- All patients will be asked to be fast, no solid food 8 hours prior to swallowing the cytosponge, can drink clear liquids up to 2 hours prior to swallowing the cytosponge
- The EoE subjects two hours prior to endoscopy will be asked to swallow the Cytosponge. Briefly, the capsule and bunched up string are swallowed with water. Two hours is chosen as the time interval because water will likely be needed to swallow the capsule and this is the standard time allowed for to last safely consume a clear liquid prior to endoscopy.
- Controls will be will have the same fasting instructions but will not be required to be having and endoscopy.
- The string is held without any tension to allow the capsule to move into the stomach. The patient holds onto the string for five minutes after ingestion to allow the capsule to dissolve in the proximal stomach, where a spherical mesh of 3 cm diameter is released.
- The back of the throat is then sprayed with 1% lidocaine and the expanded mesh withdrawn by pulling on the string with the patient's head in an extended position.
- After retrieval the string is cut and the Cytosponge containing the cytological specimen placed in preservative fluid and kept at room temperature until transportation to the laboratory.
- The whole process of administering the Cytosponge, including instructing the patient, takes less than 10 minutes.
- Following this, the clinically indicated endoscopy will be performed. The cytology specimens will be reviewed by one pathologist who will read them blindly without knowledge of the results of the biopsy specimens. The cytology specimens will be

compared to the biopsy in terms of esophageal eosinophil presence and density. A scoring system for cytology will be devised.

- Samples from the University of North Carolina will be sent to the Mayo Clinic to be reviewed by the same pathologist.

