- After the Mayo pathologist have completed their analysis, slides and part of the uncut blocks will be sent to [name] lab at the University of Cambridge looking at reproducibility of results, evaluation of the mucosal microbiome by sequencing and additional biomarker studies including RNA, methylation and protein analyses.
- We will send samples from a cell block made from the cytology fluid from the cytosponge and a portion of the primary cytosponge placed in RNAlater solution for extra-cellular RNA signature analysis with possible detection of EoE specific lumen protein products proposed to [name] lab at the University of Cincinnati.
- FFPE RNA from the concurrent biopsies at the time of the EGD if available as biopsy tissue represents the source of the dislodged cells/tissue pieces by the cytosponge. Parallel comparison will provide key clue to validate the new diagnostic approach.
- We will stain sections from esophageal biopsies and Cytosponge for the eosinophil secondary granule protein eosinophil peroxidase (EPX). This may increase the diagnostic sensitivity of the Cytosponge because EPX staining accounts for eosinophil degranulation products in addition to intact eosinophils. H+E stains and their matching EPX stains will be digitized using an Aperio slide scanner and Aperio ImageScope software will be used for quantification of EPX.
- Modification 11/24/2021 – we would also like to utilize slides from IRB15-004741 on patients that had a cytosponge and biopsy. These will undergo the EPX staining as described above. Possible samples used will be cross checked in Ptrax to ensure the subjects consented to allowing their samples to be utilized in future research and only the applicable samples will be used. Total Mayo participants to use from this study will be up to 30.

**Recruitment:** We will recruit 130 participants at Mayo there will be 180 total subjects in this trial

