**Study flow:**

- The study coordinator will look for patients being seen in Esophageal clinic with the indication of EoE or healthy controls (patients without esophageal symptoms such as GERD or dysphagia)
- When the physician has an EoE patient scheduled for a clinically indicated upper endoscopy, to diagnose or monitor their disease, these patients will be approached by the study coordinator to see if they are interested in the cytosponge study?
- Subjects willing to swallow the cytosponge that do not have esophageal symptoms will be approached by the study coordinator.
- Patients with EoE will then be scheduled to come to Gonda 9s two hours prior to the endoscopy. Healthy controls will be scheduled to come to Gonda 9 at their convenience as long as they adhere to the fasting instructions.
- The physician will have the patient swallow the Cytosponge.
- The patient holds onto the string for five minutes after ingestion to allow the capsule to dissolve in the proximal stomach, where a spherical mesh of 3 cm diameter is released.
- The back of the throat is then sprayed with 1% lidocaine and the expanded mesh withdrawn by pulling on the string with the patient's head in an extended position.
- After retrieval the string is cut and the Cytosponge containing the cytological specimen placed in preservative fluid and kept at room temperature until transportation to the laboratory.
- The whole process will take approximately 10 minutes.
- A throat swab for collection will also be performed at this time to be processed for bacterial population of the esophageal mucosa.
- Following this, the clinically indicated endoscopy will be performed. Prior to biopsies we will do a brushing of the esophagus.
- The cytology specimens will be reviewed by one Mayo pathologist who will read them blindly without knowledge of the results of the biopsy specimens.
- The cytology specimens will be compared to the biopsy in terms of esophageal eosinophil presence and density. A scoring system for cytology will be devised.
- We will do further EoE/allergy analysis with FFPE slides including EDN and tryptase staining.
- When the Mayo pathologist have completed their analysis, slides and part of the uncut blocks will be sent to [name] lab looking at reproducibility of results, evaluation of the mucosal microbiome by sequencing and additional biomarker studies including RNA, methylation and protein analyses.

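### Do the protocol's differing accounts of how the sponge is handled after retrieval undermine the pooled sensitivity and specificity?

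*Protocol*

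**What the plan says.** The Specific Aim is the sensitivity and specificity of the Cytosponge against endoscopy with biopsy, and the sponge is read for the presence and density of eosinophils.

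- **Methods:** "After retrieval the string is cut and the Cytosponge containing the cytological specimen placed in preservative fluid and kept at room temperature". **Study flow** repeats it: "the Cytosponge containing the cytological specimen placed in preservative fluid and kept at room temperature until transportation to the laboratory".
- **Methods, later bullets:** material for an outside laboratory comes from a cell block made from the cytology fluid and from "a portion of the primary cytosponge placed in RNAlater solution for extra-cellular RNA signature analysis". Study flow repeats this. Neither place gives the size of the portion or says when it is cut.
- **Data Collection:** on leaving the mouth the sponge is "washed with sterile PBS, followed by centrifugation". The supernatant is frozen, and "The pellet will also be subjected to total RNA extraction immediately after the supernatant aspiration". The same section then adds: "We will extract RNA from the remaining of FFPE sponge, aiming to acquire the RNA from the residue tissue after histological examination".
- **The two sites:** Methods states "Samples from the University of North Carolina will be sent to the Mayo Clinic to be reviewed by the same pathologist". Data Collection says that Mayo and the University of North Carolina (UNC) work to a common method and that "the data that is needed for this two center study will be collected in an identical fashion".

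Data Analysis leaves the cytology score still to be devised.

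**The concern.** In a diagnostic accuracy study, specimen preparation is part of the index test. Two sections have the sponge go into preservative after retrieval. A third has it rinsed at that same point, with the rinsed-off cells going to RNA work. A further step removes part of the sponge for RNAlater. No sentence puts these steps in order or says how the sponge is divided.

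A rinse or a cut made before fixation could change how many eosinophils reach the slide. If one site followed Methods and the other followed Data Collection, pooled sensitivity and specificity would average over two preparations, and a score devised on one might not suit the other. Specimens prepared differently could not be prepared again later. The promise of identical collection does not say which handling is meant.

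**Working it through.** The protocol gives no cell yield, loss on rinsing or cut-off for the score, so no effect on accuracy can be calculated. The check is to set the accounts side by side and ask whether they exclude one another.

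**1. Preservative or rinse first.** Methods and Study flow place the sponge in preservative after retrieval. They do not say at once, and they do not say unrinsed. Data Collection ties only the rinse to the moment of removal. A rinse followed by preservative satisfies all three sections. What is missing is a phrase linking them.

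**2. What Data Collection itself orders.** That section has two streams from one device. The first is a fresh stream, in which the rinse is spun, the supernatant frozen and the pellet extracted. The second is a fixed stream, in which RNA comes from the embedded sponge after histology. It says the RNA from the fixed sponge goes through the same experiments as the RNA from the fresh pellet, so it treats them as separate materials. An embedded sponge that has already been examined histologically must have been preserved and read first. Methods and Study flow add that material leaves for Cambridge only after the Mayo reading. The later order is therefore stated, and only the opening steps are left to inference.

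**3. Whether the rinse takes the cytology specimen.** Nothing makes the rinse pellet the specimen for cytology. Methods and Study flow say the specimen is in the sponge that goes into preservative, and Data Collection has histology done on the embedded sponge. The cytology fluid behind the cell block is not said to be the rinse, and can be read as the preservative fluid. That no pellet is kept for cytology is therefore not a contradiction.

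**4. Timing at the second site.** The word for immediate extraction counts from removal of the supernatant, not from retrieval. Only the rinse is tied to removal from the mouth. The text does not require UNC to complete the extraction before it ships specimens, and it does not describe a different route for UNC.

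**5. How many specimens could be affected.** Recruitment gives 130 participants at Mayo and 180 in total.

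- Remainder: 180 − 130 = 50. Giving these to UNC is an inference, since the protocol does not state UNC's number.
- If handling split by site: 50/180 = 0.278 (28%) prepared one way and 130/180 = 0.722 (72%) the other.
- If one order is used at both sites: 0.

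The split between eosinophilic esophagitis patients and controls at each site is not given, so the shares within sensitivity and within specificity cannot be worked out. The 28% counts specimens under a supposition. It does not measure bias.

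**The case for a change.** The strongest case for a change is that site staff must act on this text. They meet a different first step in different sections, and the protocol cites no laboratory manual that would settle it. The same extra-cellular RNA analysis is tied to cell-block and RNAlater material in Methods and Study flow but to frozen rinse supernatant in Data Collection. The planned stain for eosinophil peroxidase is valued because it detects degranulation products, and a rinse that collects luminal protein might plausibly remove some of them. The score has yet to be built, so it needs a settled preparation.

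Part of this stands. The opening steps are not linked, the RNAlater portion has no size or time, and the source material for the extra-cellular RNA work is described inconsistently. That last mismatch, the clearest of them, concerns add-on laboratory work and not the cytology reading on which the Specific Aim rests. The stain argument is an inference with no size or direction. A rinse applied to every sponge belongs to the test whose accuracy is being estimated, and a score devised on rinsed sponges is the right score for that test.

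Harm to the pooled estimates needs handling that differs between sites or patients. No section says that it does, and Data Collection says the opposite. Reporting accuracy by processing route, if more than one were ever used, is a detail that can be left to the statistical analysis plan, which is not at hand.

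**Conclusion.** The descriptions are incomplete and not well joined, but they can be read as one sequence, and the protocol commits both sites to the same collection. No bias in sensitivity or specificity is shown. The effect of a rinse is unknown in size and direction, and the number of differently prepared specimens is 0 under the protocol's own statement of common handling. The figure of 50 of 180 (28%) arises only on a split by site that the protocol disclaims.

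This rests on two assumptions: that the sections are read together and not as rival instructions, and that the commitment to identical collection is kept. On that basis, what is missing is the order of the opening steps and the size of one portion, which laboratory staff at the two sites can sensibly settle between them. Writing the order down would make the protocol clearer but would not alter the design, the estimates or their interpretation, so no change to the plan is called for.

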## **Data Handling**

A study coordinator will be responsible for collating and handling the above data into a computer accessible only through password entry by the coordinator and principal investigator of this study.

## **Data Analysis**

A scoring system will be devised for cytology scoring of eosinophil density. EPX will be quantified by a pixel count algorithm using Aperio ImageScope software and a previously validated scoring system.

## **Feasibility and Time**

It is expected to take six months to complete this study. For recruitment of patients, the Mayo Clinic has a long track record in studying patients with EoE and has over four hundred patients with this disease currently in their data base.

## **Strengths**

The strengths of this study are the relatively small group of patients required, the non-invasive and well tolerated nature of this test relative to endoscopy and biopsy and the potential efficacy of this test. Other strengths include the expertise of the investigators in eosinophilic esophagitis and the collaboration with [name], the inventor of the cytosponge, whose team has great familiarity with the administration and interpretation of the test and its results.

## **Weaknesses**

The main weaknesses of this study will be the potential inability of a patient to swallow the capsule or risk of impacting (though the capsule will dissolve and it will be easily removable).

